High resolution photographs from multiple angles will be taken in identical lighting and position with the VISIA CR and with the Fotofinder at 2 weeks, 4 weeks, 8 weeks, and 12 or 16 weeks. Additional real time video telemedicine visits will take place at 6 months and 12 months. In addition, a 72-hour safety phone call will be completed with the subject after each injection session. All visit timing will be based on the last injection session. Oneblinded dermatologist and one unblinded dermatologist will rate the patient's severity of jowling based on the Jawline Rating Scale (JRS) (1) at the 4-week, 8-week, and either 12 or 16-week visits. The patient will also rate their jowling based on the JRS as well as their satisfaction with the procedure.

Name and Intended Use of Devices and Medications

Proprietary name: JUVÉDERM VOLUMA™ XC Common name: non-animal hyaluronic acid Intended use: correction of cheek volume loss

Materials

The devices will be maintained according to the manufacturer's suggested maintenance. The devices will be utilized as packaged with only the needles that were included in the packaging and without manipulating the filler device or contents. No cannulae will be utilized for this study.

If needed for an adverse event, hyaluronidase will be utilized and will be stored according to manufacturers' specification (Hylenex recombinant hyaluronidase human injection, 150 USP units/cc).

Benefit / Risk Analysis

The benefits of participating in this study are to potentially improve moderate to severe facial volume loss leading to an aging appearance, specifically in the jowls.

Commonly reported side effects (SEs) of JUVÉDERM® injectable fillers include, but are not limited to, injection-site erythema or redness, swelling, pain, tenderness, discomfort, firmness, lumps/bumps, bruising, discoloration, and itching. As most of these risks are common to filler injection procedures, the treating physician (TI) will use his/her medical judgment to determine any necessary intervention(s).

Additional risks to undergoing a treatment like this include infection, blindness, stroke, vascular compromise, and scarring. More detailed information regarding the possible Adverse Events (AEs), safety assessments, and investigator protocol in the event of intravascular injection will be noted below.

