While rare, unintentional injection into a blood vessel has been reported for facial injections which can be serious and may be permanent. Any incidence of visual disturbances (including, but not limited to, any loss of vision, blurry vision, double vision, pain in or around the eye, blind spot or shadow in the visual field, trouble

moving eyes, dizziness, confusion, weakness or numbness of the arms or legs, changes to consciousness or alertness, difficulty speaking or speech impairment, facial drooping etc.) will be immediately reported to the treating physician and the sponsor. In the event of blindness or any ophthalmic signs or symptoms, the subjects must undergo immediate evaluation by a retinal specialist. More details pertaining to the reporting protocol and treating vascular compromise will be outlined below.

The incidence of serious adverse events associated with intravascular injection is very low. If a complication occurs, the subject will be advised to contact the study staff and treating physician immediately and the treating physician will use his/her medical judgement to determine the necessary interventions to treat the subject.

There are also unforeseeable risks or results associated with this procedure. If the subject experiences any unanticipated adverse event an additional visit and/ or report form may be required.

Vascular Compromise Procedure and Protocol

Recognition and Treatment of Vascular Occlusion:

Recognition:

Recognize vascular occlusion by a livedoid or violaceous appearance to the treatment area and/or blanching of the treatment area and/or patient pain.

Early signs:

- Blanching followed by violaceous patches in distribution of artery
- Pair
- * especially if they have had a filler treatment before and it is unusual and/or more severe in days following injection

Delayed signs:

- Violaceous or dusky reticulated patches in distribution of arteries
- Pain
- Necrosis

Arterial Compromise vs. Bruising:

- Does not typically develop yellow coloration like bruising
- Not typically round or in dependent areas like bruising

Treatment:

When vascular occlusion is suspected, it is crucial that the injection is stopped immediately and treatment is rapidly instigated. The objective is to facilitate blood flow to the affected area. The steps for treatment of a vascular occlusion are:

- 1. Immediately flood the entire treatment area with injected 200-300 U of Hyaluronidase (1.25-2.0 cc of Hylenex, 150 u/cc).

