- 2. Apply a warm compress
- 3. Massage the area.
- 4. If no reduction in violaceous or blanching appearance and/or pain after 10 minutes, apply 2% nitroglycerin paste to promote vasodilatation.
- 5. 60 min later if no improvement, reinject 200-300U of hyaluronidase.
- 6. Repeat Hourly and daily
- 7. If none of these measures work and depending on severity, institute daily hyperbaric oxygen chamber treatments.

Hyaluronidase should be injected immediately, regardless of the filler used, and administered hourly and/or daily in liberal doses where signs and symptoms are present.

When injecting hyaluronidase to treat acute ischemia, consensus recommendations are that the entire ischemic area be treated, not just the site where HA was originally injected. Doses up to 1500 U may be required to achieve reversal of vascular compromise.

References:

Recognition and Treatment of Retinal Occlusion

If patient complains of loss of vision, periorbital pain, blurred vision, ptosis, or impairment of extraocular muscle functionality immediately perform Snellen Chart Visual Acuity Calculation.

Fortunately, recent review of the literature asserted that the most common locations of injection leading to this complication were the forehead, nose and temple, and specifically the jawline was NOT involved in any single case

Nevertheless, preparations will be made in event of this catastrophic complication. There is no definitive and completely accepted protocol for treating this complication.

However, most experts recommend:

- Assess visual acuity with Snellen Chart examination
- 2. Make sure pupils are round and equal and respond to light.
- 3. Immediately arrange for transfer to a retinal surgeon office and transfer at first opportunity (surgeon or associate to drive).
- 4. Apply 1 drop of Timolol to affected eye.
- 5. Begin massage of the eye
 - a. Digital massage should start immediately

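### In step 1 of the vascular occlusion treatment, the unit range and the volume range for hyaluronidase do not convert to each other at the lower end

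*Combined protocol and SAP*

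**What the plan says.** The instruction is step 1 under Treatment in the protocol section Vascular Compromise Procedure and Protocol: "Immediately flood the entire treatment area with injected 200-300 U of Hyaluronidase (1.25-2.0 cc of Hylenex, 150 u/cc". The units, the volume and the concentration all stand in that one sentence.

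Three other places bear on it:

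- **Materials** names the same product and strength: "Hylenex recombinant hyaluronidase human injection, 150 USP units/cc".
- **Step 5 of the same list** covers a lack of response: "60 min later if no improvement, reinject 200-300U of hyaluronidase". It gives units and no volume.
- **The text after the numbered steps** allows for larger amounts: "Doses up to 1500 U may be required to achieve reversal of vascular compromise". Step 6 and that text also provide for hourly and daily repetition.

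**The concern.** When a dose is given both in units and in volume, the volume is there to spare staff a conversion. The two forms should therefore be interchangeable at the stated strength. Here they are not. A person who draws up the lowest stated volume and a person who draws up the lowest stated number of units would both be following step 1, yet would inject different amounts.

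This is an operative rescue instruction, meant to be carried out quickly, for one of the severe events that the protocol lists. An avoidable ambiguity is least welcome there. A secondary consequence is for compliance: if anyone later had to judge whether the step was followed, an injection of 1.25 cc would meet the volume range and miss the unit range.

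**Working it through.** **Inputs**

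- Unit range, step 1: 200 to 300 U.
- Volume range and concentration, step 1: "1.25-2.0 cc of Hylenex, 150 u/cc".
- Concentration, Materials: 150 USP units/cc, the same value stated separately.

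**Formulas:** units = volume × concentration; volume = units / concentration.

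**Upper end (the plan's figure reproduces)**

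- 2.0 cc × 150 U/cc = 300 U.
- 300 U / 150 U/cc = 2.0 cc.

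**Lower end (the plan's figure does not reproduce)**

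- 1.25 cc × 150 U/cc = 187.5 U, against 200 U stated.
- 200 U / 150 U/cc = 1.33 cc, against 1.25 cc stated.
- Shortfall: 200 − 187.5 = 12.5 U, and 12.5 / 200 = 6.25%.

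**Could another concentration explain it?** The lower pair implies 200 / 1.25 = 160 U/cc. The upper pair implies 300 / 2.0 = 150 U/cc. No single concentration fits both ends.

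**Could rounding explain it?** The exact lower volume, 1.333 cc, was rounded to several step sizes:

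| Rounded to nearest | Volume (cc) | Units at 150 U/cc |
|---|---|---|
| 0.01 cc | 1.33 | 199.5 |
| 0.05 cc | 1.35 | 202.5 |
| 0.1 cc | 1.3 | 195 |
| 0.25 cc | 1.25 | 187.5 |
| 0.5 cc | 1.5 | 225 |

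Of these, only the quarter-cc step gives 1.25 cc. The protocol mentions no such rounding and does not mark the volume as approximate.

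**How much of the range is affected?** The stated volumes span 2.0 − 1.25 = 0.75 cc. Volumes from 1.33 to 2.0 cc satisfy both forms. That is 0.67 cc, or 0.667 / 0.75 = 89% of the span. The conflict covers the remaining 0.083 cc.

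**The case against.** The strongest reply is that the discrepancy is real but trivial. Step 1 gives a range, and most of that range is consistent in both forms. The gap looks like a lower volume rounded to the nearest quarter cc. The protocol leaves the necessary interventions to the treating physician's judgement, has the response reassessed and the dose repeated, and contemplates up to 1500 U. Against that total, 12.5 U is 12.5 / 1500 = 0.8%. No endpoint, analysis or eligibility rule depends on the figure.

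All of this stands as an argument about weight. It does not reconcile step 1. Permission to repeat or increase a dose does not make 1.25 cc equal 200 U, and unstated rounding is not something staff can be expected to infer.

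A reader might also infer that the error recurs at each hourly reinjection. The documents do not support this. Step 5 gives units only, in the same range as step 1, and nothing tells staff to reuse the step 1 volume. The mismatch is confined to step 1.

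A mistyped digit in the 1.25 is conceivable, but nothing in the sentence points to it, and the upper end converts exactly.

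**Conclusion.** Minor, and wrong as written. At the protocol's own 150 U/cc, the stated volumes correspond to 187.5 to 300 U and the stated units to 1.33 to 2.0 cc. The disagreement is at most 12.5 U (6.25% of the lower unit figure) and arises only for volumes from 1.25 up to 1.33 cc. The conclusion rests on the stated concentration, which two sections give independently, and on the volume being meant as a conversion of the units, which is how the sentence is built.

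Three stronger readings go beyond the documents:

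- **That the volume is the wrong figure, or that the units are.** The arithmetic shows inconsistency and cannot say which was intended.
- **That a patient would be harmed by the lower amount.** Nothing in the protocol supports this, and its provision for repeat and larger doses limits the practical effect.
- **That the step governs the most serious harm foreseen.** Vascular compromise is one of several listed severe events. Blindness and stroke are listed separately, and retinal occlusion has its own procedure.

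**What to change.** The sponsor and the responsible clinicians should reconcile the unit range and the cc range in step 1 so that each converts to the other at the stated concentration. If the volume is meant as an approximation, the text should say so. If the reconciliation changes the unit range, the change should be carried through to step 5, which otherwise needs no correction. Which figures are intended is a clinical decision, and none is proposed here.

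The cost is one line in a protocol amendment and the same line in any site emergency instructions derived from it. No analysis, sample size or data collection is affected.

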Photographs will remain unretouched. One blinded dermatologist and one unblinded dermatologist will rate the patient's severity of jowling based on the Jawline Rating Scale (JRS) (1) at baseline, the 4-week, 8-week, and 12 or 16-week visits. The patient will also rate their jowling based on the JRS as well as their satisfaction with the procedure.

Analysis of Scientific Soundness of the Protocol

The proposed study has been designed to provide a valid method to analyze the safety and efficacy of facial volume replacement. Measure taken to assure that the study provides valid data are as follows:

- 1. Photographs will be taken under standardized conditions. Photographs will be taken with a VISIA CR, a device made by Canfield Scientific specifically to be utilized for clinical research to provide uniformity in patient photographs.
- 2. Adverse or unanticipated effects that occur during the course of this clinical study will be recorded and carefully analyzed as to their relationship to the treatment.
- 3. Evaluators will review individual photos without knowledge of if they are before or after photos.

Primary Outcome Measure:

The primary outcome is a reduction of 1 or more points of the Jawline Rating Scale (JRS)
 Assessment (on scale of 0 to 4) at baseline versus that at 4 weeks from the last injection (whether initial or touch-up) based on any or all of one blinded dermatologist rating, one unblinded dermatologist rating, and patient rating. (A lower number will mean a better outcome) Time Frame: Baseline to 4 weeks after last injection.

Secondary Outcome Measures

- 1. Reduction of 1 or more points of the Jawline Rating Scale (JRS) Assessment (on scale of 0 to 4) at baseline versus that at 4 weeks from the last injection based on the patients rating while looking in the mirror and at before and after photographs. A lower number will mean a better outcome. Time Frame: 4 weeks from last injection
- 2. Whether group 1 and group 2 has a higher reduction in the Jawline Rating Scale (JRS) (on scale of 0 to 4) at 4 weeks from the lastinjection compared to baseline based on ratings from one blinded dermatologist and one unblinded dermatologist. A lower number will mean a better outcome. Time Frame: 4 weeks from last injection
- 3. Whether group 1 or group 2 has a higher reduction in the Jawline Rating Scale (JRS) (on scale of 0 to 4) at 4 weeks from the last injection compared to baseline based on the patients rating while looking in the mirror and at before and after photographs. A lower number will mean a better outcome. Time Frame: 4 weeks from last injection
- 4. Jawline Rating Scale (JRS) Assessment on scale of 0 to 4 at 4 weeks: One blinded dermatologist and one unblinded dermatologist will rate the patient's severity of jowling based on the Jawline Rating Scale (JRS). The patient will also rate their jowling based on the Jawline Rating Scale (JRS). The scale is on a rating of 0 to 4. A lower number will mean a better outcome. [Time Frame: 4 weeks]
- 5. Jawline Rating Scale (JRS) Assessment on scale of 0 to 4 at 8 weeks: One blinded dermatologist and one unblinded dermatologist will rate the patient's severity of jowling based on the Jawline Rating Scale (JRS). The patient will also rate their jowling based on the Jawline Rating Scale (JRS). The scale is on a rating of 0 to 4. A lower number will mean a better outcome. [Time Frame: 8 weeks]
- 6. Jawline Rating Scale (JRS) Assessment on scale of 0 to 4 at 12 or 16 weeks: One blinded dermatologist and one unblinded dermatologist will rate the patient's severity of jowling based on the Jawline Rating Scale (JRS). The patient will also rate their jowling based on the Jawline Rating Scale (JRS). The scale is on a rating of 0 to 4. A lower number will mean a better outcome. [Time Frame: 3 months from last treatment]
- Incidence of abnormal eye exam (Confrontational Visual Fields Exam) findings (Safety):
 Ophthalmologic exams that include Confrontational Visual Fields Exam will be performed prior to any
 treatment, 30 minutes after treatment, and at all follow up in-person visits. [Time Frame: up to 18
 months]
- 8. Incidence of abnormal eye exam (Snellen Eye Exam) findings (Safety):
 Ophthalmologic exams that include Snellen Eye Exam will be performed prior to any treatment, 30 minutes after treatment, and at all follow up in-person visits. [Time Frame: up to 18 months]
- 9. Incidence of abnormal eye exam (Ocular Motility Exam) findings (Safety):
 Ophthalmologic exams that include Ocular Motility Exam will be performed prior to any treatment,
 30 minutes after treatment, and at all follow up in-person visits. [Time Frame: up to 18 months]
- 10. Incidence of abnormal cranial nerves II, III, IV and VII assessments findings (Safety):

 To further assess vision and oculomotor function, cranial nerves II, III, IV, and VII will be assessed
 (left and right sides separately). To assess lower face function, cranial nerves V, VII, IX, X, and XII will be assessed. These exams will be performed prior to any treatment, 30 minutes after treatment, and at all follow up visits. [Time Frame: up to 18 months]
- 11. Adverse events:

Adverse events will be recorded until 12 months after last treatment. [Time Frame: up to 12 months after last treatment]

Adherence to Protocol

The investigator will review the contents of this protocol. Any alterations to the protocol will be made in writing to the sponsor.

Records and Reports

Data from the pre-treatment evaluation, the treatment procedure, complications, if any, the post-treatment evaluation and all follow up evaluations will be recorded on the clinical data forms prepared for the study.

All records and reports concerning the clinical study will be forwarded to the Sponsor within a reasonable amount of time. The Investigator shall retain copies of all documentation for a period of two years following the date on which the entire clinical investigation is terminated or discontinued.

Confidentiality

This study is confidential. Information made public regarding subjects enrolled in this study will not disclose the name of any individual.

Information made public regarding subjects enrolled in this study will not disclose the name of any individual. All our research records are stored securely in locked cabinets and password protected computers. Only a few people who are closely concerned with the research will be able to view information from participants. Data is coded.

The results of this study will be provided to Allergan, including photographs, but no identifying subject information will be disclosed.

The results of this research study may be presented at scientific or medical meetings or published in scientific journals. Subject identities will not be disclosed in any of these meetings or publications.

A description of this clinical trial will be available on http://www.ClinicalTrials.gov, as required by

U.S. Law. This Web site will not include information that can identify subjects. At most, the Web site will include a summary of the results.

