^{*} Safety Eye Assessments will be performed prior to treatment and 30 minutes after treatment

^{**}Patient diary to be completed daily by email for 30 days following treatment

^{***}No Retreatment done per patient and/or physician

advanced Jowl Improvement with Injectable Fillers: Jawline Injections alone vs Jawline and Cheek Injections

Blinded Physician Assessment

Patient Number	Date:			
Baseline or Date pos Baseline or Date Pos	t 1 st Injection: Baselin st 2 nd Injection: Baselin	e4w8w_ ne4w8w_	12 week 16 12 week 16	16 week sweek
No.	OMAZ -	- CMAZ	CMAZ	SMB2
OMerz O	- OMerz	CMerz CMerz	GMerz S	©Merz.
0	1	2	3	4
No sagging	Mild sagging	Moderate sagging	Severe sagging	Very severe sagging
pictured above, put a	etructions: Without reference X by the value you 3 4	feel represents the a		
the patient prior to in	jection and the photogoutting an X by the varied	graph of the patient to	oday, please evaluate	
Comments:				
Blinded Physician: Date:	Name	Sig	nature	

advanced Jowl Improvement with Injectable Fillers: Jawline Injections alone vs Jawline and Cheek Injections 10001

Subject Self-Assessment of Results

Patient Number				
Date:				
Baseline or Date post Or: Date Post 2 nd Injection	-	line 4 w 8 8w 12 w_		16 week
©Merz ©Merz	OMerz	SMerz	CMerz CMerz	CMerz CMerz
3	1	1	3	1
0	1	2	3	4
No sagging	Mild sagging	Moderate sagging	Severe sagging	Very severe sagging
Grading of Jowls Instructured above, put an				
1 2	34	_ 5		
Grading of Jowls by p yourself prior to inject putting an X by the va	ion and the photogra	ph of yourself today, p	olease evaluate your	
Much improved Improved No change Worse Much Worse	-			
Comments:				
Signature of Coordi	nator	Date:		

	Iowl/Jawline Study Iumber	10001-Patient Diary		Date
	e treatment			
many da	ys it has been since	= :	ne questions v	patient number, the date, and how which require to answer mild,
• N	Moderate: minimal,	and/or local or noninva out not immediately life	sive intervent	only; no intervention needed tion needed nospitalization or prolongation of
Have y	you experien	ced any of the fo	ollowing s	symptoms?
	oderate to Severe Di yes was it Mild	zziness Moderate		NO
	onfusion yes was it Mild	Moderate		NO
		s in your arms or legs Moderate		
	nanges to consciousn yes was it Mild	ess or alertness Moderate		NO
		eech impairment Moderate		
If		Moderate	Severe	
				bove questions, pleas
 1811 91 2 2 2 2 2 2 2 2 2 2 2 2 2 2 2 2 2 	L1 and seek i	mmediate medi	cal attent	ion.

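### The protocol promises photograph review masked to before and after, but the blinded rater's own form undermines that masking and no available section secures it

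*Combined protocol and SAP*

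**What the plan says.** Item 3 under Analysis of Scientific Soundness of the Protocol is one of three measures listed in support of valid data: "Evaluators will review individual photos without knowledge of if they are before or after photos". It does not say which evaluators it covers.

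Under Data Analysis and Primary Outcome Measure, a blinded dermatologist, an unblinded dermatologist and the patient each give a JRS grade. The primary outcome is a fall of at least 1 point between baseline and 4 weeks after the last injection, touch-up included, judged on any or all of the three ratings. Secondary outcomes 2 and 4 to 6 also use the blinded rating.

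The Blinded Physician Assessment form is partly broken in the available text, but its order can be read:
- A header with a date line and time-point fields ("Baseline or Date pos" is the start of one) for baseline and 4, 8, 12 and 16 weeks, after a first or second injection.
- The 0–4 grade, with an instruction that begins "Without reference" and then breaks off.
- A second item, of which "the patient prior to in" and "graph of the patient to" survive, setting the pre-injection state against the current photograph.
- The rater's sign-off, "Blinded Physician: Date".

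The Subject Self-Assessment form has the same two parts in clearer text ("ph of yourself today, p") and a coordinator line ("Signature of Coordi").

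Both Appendix 1 schedules mark the blinded evaluation at Screening and at three follow-up visits. They mark no photography at Screening; the first photographs are at the treatment visit.

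**The concern.** Every patient is treated and the primary outcome is a change from baseline with no untreated control. Masking the rater to time is therefore the main protection against grades drifting toward the expected improvement. The protocol claims that protection in item 3, yet the form designed for the blinded rater shows the visit and then asks for a before/after judgement. If the form is used as drafted, the safeguard may not be delivered for the blinded dermatologist's part of the primary outcome and of secondary outcomes 2 and 4 to 6.

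**Working it through.** The documents give no figure to reproduce here. The check compares the sections and then counts.

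**1. Item 3 against the form header.** Item 3 requires that the rater not know whether an image is before or after. The header names the visit on the same sheet as the grade. In the available text the only signature line on this form is the blinded physician's own, whereas the patient's form has a coordinator line, so the rater evidently handles the sheet. The documents do not say whether the header is filled in before grading, or by whom. The header can unmask the grade; it is not shown to do so.

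**2. Item 3 against the comparison.** A rater cannot compare a pre-injection photograph with today's without knowing which is which. This conflict with item 3 is direct. The item comes after the grade, so it cannot affect the grade already given on that sheet.

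**3. How far the comparison can carry over.**
- No touch-up: the primary grade is the 4-week grade, given before any post-treatment comparison. Only the later grades (8 weeks; 12 or 16 weeks) can be affected.
- Touch-up: the retreatment schedule marks a blinded evaluation at the 4-week visit, where retreatment takes place, and again afterwards. The primary grade, 4 weeks after the touch-up, then follows a sheet on which the comparison was already due. Here carry-over can reach the primary outcome. The number of such patients is not stated.

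**4. Search for a safeguard.** No available section provides for undated images, random order, completion of the header by someone else, or locking of the grade before the comparison. The statement under Confidentiality that data are coded concerns identity, not time point. The Protocol Summary, Data Analysis and both schedules tie the blinded rating to named visits.

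**5. Size per shifted grade.** With 16 patients (Study Design, Scope), one blinded grade moved across the 1-point threshold changes the blinded-rater response rate by 1/16 = 0.0625, or 6.25 points. For the primary outcome:

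| Reading of *any or all* | A shifted blinded grade changes the patient's result when |
|---|---|
| Any one rater suffices | neither other rater scored a response |
| All three required | both other raters scored a response |
| Each rater reported separately | always, for the blinded rater's result |

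Under the first two readings the effect is 0 or 6.25 points per such patient, and it is 0 whenever the other two raters disagree.

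**6. Number of blinded evaluations.** By the schedules, 4 per patient × 16 = 64. The primary outcome uses 2 per patient (baseline and 4 weeks after the last injection), 2 × 16 = 32. The Protocol Summary times all visits from the last injection. If a touched-up patient is rated at baseline, 4 weeks after the first injection, and three times after the second, that is 5 ratings; the upper bound, assuming all 16 are touched up, is 5 × 16 = 80.

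**7. Screening.** One of the 4 marks (16 of 64) is at Screening, with no photography marked there. Pre-Procedure Evaluation mentions pre-treatment photographs without naming a visit. This needs reconciling with photograph-based grading; it does not prove that the baseline grade is given live.

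**The case against.** Every case report form needs a time-point field to link the data, and a signature does not show that the field was filled in before grading. Scheduling a rating at a visit labels the time point without proving that the rater knew it. The instruction beginning "Without reference" suggests that the grade was meant to stand alone, and its remainder is lost. The comparison is not a listed outcome. Some operational detail may reasonably be left out of a short protocol.

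Much of this stands, and it rules out three stronger readings that a reader might infer:
- *The blinded dermatologist is in fact unmasked.* The documents do not establish this.
- *The comparison contaminates the primary outcome in everyone.* Its position after the grade limits that route to touched-up patients.
- *Only the blinded dermatologist was ever meant to be masked to time.* Item 3 speaks of evaluators in the plural, and only one dermatologist is called blinded. The other may be unblinded to group yet covered by item 3.

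What does not stand is the view that this is merely missing detail. The form positively asks for something item 3 excludes, and grading without reference to another image does not hide which visit is being graded.

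**Conclusion.** The point holds as a gap between a stated safeguard and the form meant to deliver it: masking to time is promised, undermined by the form, and secured nowhere in the available text. It should be fixed. Confidence is moderate, because the form text is broken and a few passages are unavailable; their location (around the retinal-occlusion section and after the pain form) makes a masking procedure there unlikely but not impossible.

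No size of bias can be derived. The scale is 6.25 points of blinded-rater response rate per shifted grade, assuming all 16 patients are analysed, with the effect on the primary outcome depending on the any-or-all rule.

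A reader might also infer that the Group 1 versus Group 2 comparison is unmasked. The documents do not support that: date and visit fields are common to both groups and do not reveal allocation.

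**What to change.** - Have the same blinded dermatologist grade the JRS from coded, undated photographs in random order with time points mixed.
- Remove the date and visit fields from the rater's copy; existing staff other than the rater hold the code and add them afterwards.
- Move the before/after comparison to a separate form, completed only after that rater's JRS grades are locked.
- State which evaluators item 3 covers. It cannot cover the patient, who rates from a mirror and before and after photographs, and it should not be narrowed to exclude the unblinded dermatologist without a stated reason.
- Reconcile the blinded-evaluation mark at Screening with photograph-based grading, and keep the entry grading under Patient Selection separate from the coded baseline grade.

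The cost is form and schedule wording and the coding of about 64 photograph sets by existing staff, more if touched-up patients are rated at extra visits. The rater stays the same and no visits are added. The downside is that blinded grades become available later.
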